6.1.5. Management of Infusion-related Reactions

Infusion-related reactions (IRRs) are systemic reactions related to daratumumab administration (IV or SC). Subjects in Arm B should be carefully observed during daratumumab administrations. Trained study staff at the clinic should be prepared to intervene in case of any infusion reactions occurring, and resources necessary for resuscitation (eg, agents such as epinephrine and aerosolized bronchodilator, also medical equipment such as oxygen tanks, tracheostomy equipment, and a defibrillator) must be available at the bedside. Attention to staffing should be considered when multiple subjects will be dosed at the same time.

If an infusion-related reaction develops during daratumumab administration, then the administration should be paused. Subjects who experience adverse events during the daratumumab administration must be treated according to the investigator's judgment and best clinical practice. The following guidelines may apply:

- Subjects should be treated with acetaminophen, antihistamine, or corticosteroids. Intravenous saline may be indicated. For bronchospasm, urticaria, or dyspnea, subjects may require antihistamines, oxygen, corticosteroids, or bronchodilators. For hypotension, subjects may require vasopressors.
- In the event of a life-threatening infusion-related reaction (which may include pulmonary or cardiac events), or anaphylactic reaction, daratumumab should be discontinued and no additional daratumumab should be administered to the subject. Aggressive symptomatic treatment should be applied.

For subjects treated with daratumumab IV, if an infusion is paused, then a longer-than-anticipated infusion time may occur. Overnight stays at the hospital because of slow infusion times should not be reported as a serious adverse event. However, if the underlying cause of the delayed infusion time is an adverse event or serious adverse event, then that should be reported as such.

6.1.5.1. Infusion-Related Events of Grade 1 or Grade 2

If the investigator assesses a Grade 1 or 2 adverse event to be related to daratumumab, then daratumumab administration should be paused. When the subject's condition is stable, the daratumumab administration may be restarted at the investigator's discretion. For subjects treated with daratumumab IV, upon restart, the infusion rate should be half of that used before the interruption. Subsequently, the infusion rate may be increased at the investigator's discretion.

If the subject experiences a Grade 2 or higher event of laryngeal edema or a Grade 2 or higher event of bronchospasm that does not respond to systemic therapy and does not resolve within 6 hours from the onset, then the subject must be withdrawn from treatment.

6.1.5.2. Infusion-Related Reactions of Grade 3 or Higher

For infusion-related adverse events that are Grade 4, daratumumab should be stopped and treatment with daratumumab will be discontinued for that subject.

For infusion-related adverse events that are Grade 3, the daratumumab administration must be stopped, and the subject must be observed carefully until the resolution of the adverse event or until the intensity of the event decreases to Grade 1, at which point the daratumumab may be restarted at the investigator's discretion. For subjects treated with daratumumab IV, upon restart, the infusion rate should be half of that used before the interruption. Subsequently, the infusion rate may be increased at the investigator's discretion.

If the intensity of the adverse event returns to Grade 3 after restart of daratumumab, then the procedure described in this section may be repeated at the investigator's discretion. Should the intensity of the adverse event increase to Grade 3 for a third time, then treatment with daratumumab will be discontinued for that subject.

6.1.5.3. Injection-Site Reactions

In clinical studies, SC administration of daratumumab was associated with local injection site reactions, such as induration and erythema, in some subjects. The reactions usually resolved within 60 minutes. Local injection-site reactions should be managed per institutional standards.

6.2. Lenalidomide (Arm A and Arm B)

Lenalidomide will be self-administered at a dose of 25 mg PO each day on Days 1 through 21 of each 28-day cycle for subjects with creatinine clearance >50 mL/min. If creatinine clearance is between 30 and 50 mL/min, the dose of lenalidomide will be 10 mg every 24 hours. Once the creatinine clearance is >50 mL/min during the course of the treatment, lenalidomide can be increased to 25 mg. In both treatment arms, subjects will continue on lenalidomide until progression of disease or unacceptable toxicity. Subjects in Arm B who discontinued treatment with Rd at 24 months may re-start treatment with Rd as per Amendment INT-4.

On daratumumab administration days, it is recommended that lenalidomide should be administered either prior to or at the same time (preferred) as the premedications.

If a daily lenalidomide dose is missed, it may be taken if <12 hours have elapsed since the time that it should have been taken. If the next dose is scheduled to be taken within 12 hours, the missed lenalidomide dose should be skipped.

6.3. Dexamethasone (Arm A and Arm B)

Dexamethasone (or equivalent in accordance with local standards; see Attachment 6 for conversion table) will be administered at a total dose of 40 mg weekly. For subjects older than 75 years or underweight (BMI <18.5), the dexamethasone dose may be administered at a dose of 20 mg weekly. In both treatment arms, dexamethasone will be administered until the subject experiences disease progression or unacceptable toxicity, whichever comes first. Subjects in Arm B who discontinued treatment with Rd at 24 months may re-start treatment with Rd as per Amendment INT-4.

On days when subjects in Arm B receive a dose of daratumumab, dexamethasone will not be self-administered but instead will be administered in the clinic. In this setting, dexamethasone will be utilized as the treatment dose of steroid for that particular day, as well as the required pre-medication prior to daratumumab administration.

If a weekly dexamethasone dose is missed, it may be taken if <4 days have elapsed since the time that it should have been taken. If the next dose is scheduled to be taken within 3 days, the missed dexamethasone dose should be skipped.

6.4. Dose Delays and Dose Modification

Subjects who need to discontinue treatment with any one component of study treatment (lenalidomide, dexamethasone, or daratumumab) may continue to receive treatment with the other components of study treatment, as assigned.

6.4.1. Daratumumab Dose Modification

Dose modification of daratumumab is not permitted, but dose delay is the primary method for managing daratumumab-related toxicities.

6.4.1.1. Daratumumab-Related Toxicity Management

Refer to Section 6.1.4 for details on management of infusion-related reactions. ONLY if any of the following criteria are met and the event cannot be ascribed to lenalidomide, the daratumumab administration must be held to allow for recovery from toxicity. The criteria for a dose delay are:

- Grade 4 hematologic toxicity
- Grade 3 thrombocytopenia with bleeding
- Febrile neutropenia
- Neutropenia with infection, of any grade
- Grade 3 or higher nonhematologic toxicities with the following exceptions:
 - Grade 3 nausea that responds to antiemetic treatment within 7 days
 - Grade 3 vomiting that responds to antiemetic treatment within 7 days
 - Grade 3 diarrhea that responds to antidiarrheal treatment within 7 days
 - Grade 3 fatigue that was present at baseline or that lasts for <7 days after the last administration of daratumumab
 - Grade 3 asthenia that was present at baseline or that lasts for <7 days after the last administration of daratumumab

Other than on Day 1 of a cycle, if a daratumumab dose does not commence within the prespecified window (Table 3) of the scheduled administration date, then the dose will be considered a missed dose. Administration may resume at the next planned dosing date. A missed dose will not be made up.

Table 3: Daratumumab-Related Toxicity Management

Cycles	Frequency	Dose Held	Dosing Re start
1 and 2	Weekly (q1wk)	>3 days	next planned weekly dosing date
3 to 6	Biweekly (q2wks)`	>1 week	next planned biweekly dosing date
7+	Every 4 weeks (Q4W)	>2 weeks	next planned every 4 weeks dosing date

Doses of daratumumab may be delayed up to 4 weeks (Cycle 1 to Cycle 6) or up to 6 weeks (Cycle 7 and beyond). Day 1 of a cycle should not be skipped; however, Day 1 of a cycle may be delayed, and Day 1 of subsequent cycles should be adjusted accordingly to maintain the 28-day cycle duration. However, if a within-cycle dose is delayed, then the dates of the subsequent within-cycle doses should not be adjusted. Any adverse event deemed to be related to daratumumab that requires a dose hold of more than 4 weeks (Cycle 1 to Cycle 6) or more than 6 weeks (Cycle 7 and beyond) will result in permanent discontinuation of daratumumab. If a dose delay occurs, then pharmacokinetic and pharmacodynamic assessments should be performed on the actual administration day of daratumumab, not on the original scheduled administration day.

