6.4.1.2. Daratumumab Interruption or Missed Doses

A daratumumab dose that is held for more than the permitted time (Table 3) from the per-protocol administration date for any reason other than toxicities suspected to be related to daratumumab should be brought to the attention of the Sponsor at the earliest possible time. Subjects whose dose was delayed for more than 4 weeks (Cycle 1 to Cycle 6) or more than 6 weeks (Cycle 7 and beyond) should have study treatment discontinued, unless, upon consultation with the sponsor and the review of safety and efficacy, continuation is agreed upon. Infusion-related reactions may occur upon re-initiation of daratumumab after a prolonged delay in treatment and subjects receiving daratumumab SC should have prolonged observation following the first dose post re-initiation.

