10.2. Discontinuation of Study Treatment

If a subject's study treatment must be discontinued before the end of the treatment regimen, this will not result in automatic withdrawal of the subject from the study. After treatment discontinuation, the subject will move into the Follow-up Phase. The End-of-Treatment Visit and Follow-up visit assessments should continue as specified in the Time and Events Schedule. If study treatment is discontinued for a reason other than disease progression, then disease evaluations will continue to be performed as specified in the Time and Events Schedule.

Subjects who need to discontinue treatment with any one component of study treatment (lenalidomide, dexamethasone, or daratumumab) may continue to receive treatment with the other components of study treatment, as assigned.

A subject's study treatment will be discontinued if:

- The investigator believes that for safety reasons (eg, adverse event) it is in the best interest of the subject to discontinue study treatment
- The subject becomes pregnant or a positive pregnancy test does occur
- The subject (or the subject's legally acceptable representative) withdraws consent for administration of study treatment
- The subject initiates treatment with a prohibited medication
- The subject received concurrent (non-protocol) treatment for multiple myeloma
- The subject experiences unacceptable toxicity, including infusion-related reactions described in Section 6.1.5
- The subject's dose of daratumumab is held for more than 4 weeks in Cycles 1- 6 or for more than 6 weeks in Cycle 7 and beyond (unless Sponsor approves continuation)

• The subject experiences disease progression (please see below). Relapse from CR is not considered as disease progression

A subject who experiences a second primary malignancy that can be treated by surgery may continue to receive the assigned study treatment and the subject should continue to be followed for subsequent progression of multiple myeloma. Subjects who require radiation therapy for treatment of second primary malignancy must have study treatment discontinued unless, upon consultation with the Sponsor and review of data, continuation is agreed upon. Subjects who require systemic treatment of a new malignancy must end study treatment but should continue to be followed for PFS2 and OS.

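### After a prolonged daratumumab hold the protocol disagrees on which drugs stop and whether sponsor agreement applies, and Table 3 disagrees with the text on a late Cycle 7+ dose

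*Protocol*

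**What the plan says.** **What stops after a long hold**

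- Protocol 6.4.1.1 sets the early-cycle trigger as "Any adverse event deemed to be related to daratumumab that requires a dose hold of more than 4 weeks (Cycle 1 to Cycle 6"); from Cycle 7 the limit rises to 6 weeks. The consequence is that it "will result in permanent discontinuation of daratumumab". No sponsor exception is stated.
- Protocol 6.4.1.2 opens with holds for reasons other than suspected daratumumab toxicity, which must be reported to the sponsor. Its next sentence says that subjects delayed past the same thresholds "should have study treatment discontinued, unless, upon consultation with the sponsor and the review of safety and efficacy, continuation is agreed upon".
- Protocol 10.2 lists the conditions under which a subject's "study treatment will be discontinued if" they occur. One is that the "dose of daratumumab is held for more than 4 weeks in Cycles" 1 to 6, or for more than 6 weeks later, unless the sponsor approves continuation. The cause of the hold is not restricted.
- Section 6 reserves study drug for daratumumab and uses study treatment for all three drugs. It also has a parallel 4/6-week rule, with sponsor consultation, triggered by a delay of study treatment and not tied to one arm.
- Protocol 6.4 says a subject who must stop one component "may continue to receive treatment with the other components of study treatment, as assigned". Section 10.2 repeats this just above its discontinuation list.

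**A late dose from Cycle 7 onward**

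- The text of 6.4.1.1 exempts Day 1 from the missed-dose rule, states "Day 1 of a cycle should not be skipped", and lets Day 1 be delayed with later cycles moved accordingly. The longest delay allowed is 6 weeks.
- The 7+ row of Table 3, in the same section, sends a dose held more than 2 weeks to the "next planned every 4 weeks dosing date". Section 6.1.2 and the dose administration schedule both point sites to Table 3 for dosing windows.

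**The concern.** Because Section 6 defines the terms, the difference between stopping daratumumab and stopping study treatment is one drug against three. For one event, 6.4.1.1 and 10.2 give different defaults for lenalidomide and dexamethasone, and different answers on whether the sponsor may agree to daratumumab continuing.

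This matters beyond dosing. Under 3.1 and 9.1.4 the Follow-up Phase starts only when all study treatments have stopped. Under Protocol 12.3.1 and SAP 5.1 the adverse event window runs for 30 days from the last study treatment. Two sites handling the same hold differently would record different exposure, a different phase and a different safety window. Only the DRd arm can be affected, since only that arm receives daratumumab.

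The second conflict concerns whether a late maintenance dose is given late or dropped. It bears on subjects still on treatment: Attachments 11 and 12 of Amendment 9 refer dosing back to Section 6.

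**Working it through.** The documents state no figure to reproduce here, and no sample size, power or alpha calculation enters. The check sets the rules side by side and adds simple schedule arithmetic.

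**Step 1. The stopping rules for one case.** Take a 5-week hold in Cycle 4 for a daratumumab-related adverse event (35 days, above the 28-day limit).

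| Section | Drugs stopped by default | Sponsor exception stated? |
|---|---|---|
| 6.4.1.1 | daratumumab (1) | no |
| 10.2, hold criterion | daratumumab, lenalidomide, dexamethasone (3) | yes |
| 6.4.1.2, second sentence, if it covers toxicity holds | all 3 | yes |
| 6.4, and the component rule in 10.2 | only the component that must stop | not addressed |

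Two differences remain:

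- *Default for the other two drugs.* 10.2 stops them unless the sponsor agrees. 6.4.1.1 does not mention them, and the component rule lets them continue.
- *Reach of the exception.* 10.2 lets the sponsor approve continuation of study treatment, which includes daratumumab. 6.4.1.1 calls the stop permanent.

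**Step 2. Is every dose from Cycle 7 a Day 1 dose?** The dose administration schedule shows daratumumab on Days 1, 8, 15 and 22 in Cycles 1–2, Days 1 and 15 in Cycles 3–6, and Day 1 only from Cycle 7. Over the first year:

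- 13 cycles × 28 days = 364 days
- doses = 2 × 4 + 4 × 2 + 7 × 1 = 8 + 8 + 7 = 23

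This matches the 23 first-year doses in Protocol 3.1. So every Cycle 7+ dose is a Day 1 dose, and the 7+ row of Table 3 covers only doses that the adjacent text exempts from the missed-dose rule.

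**Step 3. What happens to a late Cycle 7+ dose?** Call the scheduled date day 0 and suppose the subject is ready on day 21, after a 3-week hold. That exceeds the 14 days in Table 3 and is within the 42 days in the text.

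- Text: give the dose on day 21 and move later cycles; the next doses fall on days 21 + 28 = 49 and 49 + 28 = 77.
- Table 3, read on the original calendar: restart on day 28, then days 56 and 84. The day-0 dose is dropped.

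The readings diverge for any hold of more than 14 and up to 42 days. The permitted 42-day delay is also longer than the 28-day dosing interval, so a delay the text allows can run past the date on which Table 3 would restart.

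**Step 4. What depends on the reading?**

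- *Follow-up Phase:* starts at once if all three drugs stop, but not while lenalidomide or dexamethasone continues.
- *Adverse event window:* ends 30 days after the last study treatment, so it closes earlier if all three stop. After the final CSR cut-off, Attachment 11 ties routine serious-event collection to the last dose of study drug, so this consequence mainly concerns the earlier period.
- *Disease evaluations:* under 3.1, 9.1.4 and 10.2 these continue to progression when treatment stops for another reason. Scheduled PFS assessments are the same on either reading.

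**The case against.** The best defence is that the sections have different scopes and can be followed together.

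**Scope.** 6.4.1.1 deals with related toxicity, and 6.4.1.2 opens with holds for other reasons; its stopping sentence can be read as continuing that subject. This is a fair reading, so 6.4.1.2 alone does not establish the conflict. But that sentence carries no express limit, and the 10.2 criterion applies to any daratumumab hold. The conflict between 6.4.1.1 and 10.2 stands.

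**Joint compliance.** A reader might infer that no site can satisfy all the passages. The documents do not support that. A site that stops daratumumab permanently and obtains sponsor agreement to continue the other two drugs complies with 6.4, 6.4.1.1, 6.4.1.2 and 10.2 together. What is missing is an instruction to take that course, as opposed to stopping everything or seeking agreement to resume daratumumab.

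**Sponsor role.** A reader might also infer that 6.4.1.1 rules out consulting the sponsor. It is silent. The question left open is whether the 10.2 exception extends to daratumumab after related toxicity.

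**Cycle 7+.** It would be too strong to say that Day 1 can never be skipped, or that Table 3 forces every dose held over 2 weeks to be dropped. The text says should not, and it switches off the missed-dose consequence for Day 1. The next planned date might mean the re-set Day 1, and the row still serves as the sponsor-notification threshold in 6.4.1.2. This weakens the conflict without removing it: the row prints a restart instruction that differs from the text beside it, and other sections send sites to that table.

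**Consequence.** Subjects still on treatment under Amendment 9 (July 2021) are very likely past Cycle 6, since the primary cut-off was September 2018, so the Cycle 1–6 limb is largely historical. Attachment 11 also lets the investigator stop treatment. Both points limit the practical reach.

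**Conclusion.** The point holds as an inconsistency in rules that are in the current text of Amendment 9.

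1. For a daratumumab-related hold beyond 4 or 6 weeks, 6.4.1.1 and 10.2 differ on the default for lenalidomide and dexamethasone (one drug stopped against three) and on whether sponsor agreement can cover daratumumab. The unrestricted sentence in 6.4.1.2 adds to the ambiguity.
2. For a Cycle 7+ dose held more than 2 and up to 6 weeks, the text delays the dose and Table 3 points to the next planned date.

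The documents do not say how many subjects or doses are affected; the first part cannot reach beyond the DRd arm, planned at 365 subjects. The conclusion rests on Section 6's definition of study treatment applying throughout, and on reading the planned date in Table 3 on the original calendar.

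A reader might go further and infer a bias in PFS or a loss of power. The documents do not support that: disease evaluations continue after treatment stops, and nothing here touches the event targets or alpha. What can vary by site is the set of drugs stopped, the start of the Follow-up Phase and the adverse event window. The reconciliation is worth making, but it does not threaten the primary result.

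**What to change.** The sponsor should reconcile Section 6 (the parallel delay rule), 6.4, 6.4.1.1 (text and the 7+ row of Table 3), 6.4.1.2 and 10.2 so that one consistent rule states:

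- which components stop when daratumumab is held past the thresholds;
- whether sponsor agreement applies after daratumumab-related toxicity and, if so, to which drugs;
- whether 6.4.1.2 is limited to holds for other reasons;
- how a late dose from Cycle 7 is handled, with Table 3 and the text saying the same thing.

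Which rule is clinically right is for the sponsor and its medical advisers; none is proposed here.

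The cost is wording in five sections and one table row, submitted as a protocol amendment under Section 17.1. Sample size, event targets, alpha allocation and the primary analysis are unchanged. If site practice has already varied, the study report could state how prolonged holds were handled in the DRd arm.

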6.4.1.2. Daratumumab Interruption or Missed Doses

A daratumumab dose that is held for more than the permitted time (Table 3) from the per-protocol administration date for any reason other than toxicities suspected to be related to daratumumab should be brought to the attention of the Sponsor at the earliest possible time. Subjects whose dose was delayed for more than 4 weeks (Cycle 1 to Cycle 6) or more than 6 weeks (Cycle 7 and beyond) should have study treatment discontinued, unless, upon consultation with the sponsor and the review of safety and efficacy, continuation is agreed upon. Infusion-related reactions may occur upon re-initiation of daratumumab after a prolonged delay in treatment and subjects receiving daratumumab SC should have prolonged observation following the first dose post re-initiation.

6.4.2. Lenalidomide Dose Reductions

Dose adjustments of lenalidomide will follow the approved labeling as follows:

• Starting dose: 25 mg

• Dose level 1: 15 mg

• Dose level 2: 10 mg

Dose level 3: 5 mg

Dose adjustments should be based on the highest grade of toxicity that is ascribed to lenalidomide. After initiation of lenalidomide, subsequent lenalidomide dose adjustment is based on individual subject treatment tolerance. If the investigator determines that an adverse event may be related to lenalidomide, dose adjustment can be done even if not specified in this protocol. In the event of a dose adjustment, lenalidomide doses maybe re-escalated at the investigator's discretion.

